1. PROTOCOL SUMMARY

1.1. Synopsis

Name of Investigational Product(s) (IP): Reldesemtiv	
Name of Active Ingredient(s): CK-2127107	
Protocol Title: A Phase 3, Open-Label Extension of COURAGE-ALS (CY 5031)	
Protocol Number: CY 5032	
Protocol Name: COURAGE-ALS OLE	
Phase of Development: Phase 3	

Rationale:
 
Reldesemtiv, a fast skeletal muscle troponin activator, is being investigated as a potential therapy to slow the decline of skeletal muscle function in patients with ALS. Patients who have completed the Phase 3 clinical trial (COURAGE-ALS [CY 5031]) of reldesemtiv in patients with ALS may continue to receive reldesemtiv in the open label extension (OLE), CY 5032. During the last 24 weeks of dosing in CY 5031, all patients receive open-label reldesemtiv; consequently, all patients eligible for and entering CY 5032 will have already demonstrated acceptable tolerance of reldesemtiv when they begin dosing. The OLE permits patients to continue to receive reldesemtiv after completion of CY 5031. The study will extend the overall duration of long-term safety, tolerability, and durability of effect during treatment of patients with ALS with reldesemtiv.
	
Objectives and Endpoints:	
Objectives	Endpoint(s)
Primary	

 To assess the long-term safety and tolerability of reldesemtiv in patients with ALS 	
 The incidence of adverse events (AEs) in the patient population
Secondary	

 To assess the long-term effect of reldesemtiv on ALSFRS-R functional outcomes and hospitalization by comparing early-start to delayed-start groups from CY 5031 	
 Combined assessment of change in ALSFRS-R total score, time to dependence on assisted ventilation (use non-invasive or invasive ventilation for ≥ 22 hours per day for ≥ 10 consecutive days), and survival time from baseline of CY 5031 through CY 5032 Week 48 and from Week 24 of CY 5031 through CY 5032 Week 48 Time to the first occurrence of dependence on assisted ventilation or death from Day 1 in CY 5031 through CY 5032 Week 48 Changes in ALS Functional Rating Scale – Revised (ALSFRS-R) total score from baseline of

	
CY 5031 through CY 5032 Week 48 and from Week 24 of CY 5031 through CY 5032 Week 48
 
 • Slopes of the changes in ALSFRS-R total score from baseline of CY 5031 through CY 5032 Week 48 and from Week 24 of CY 5031 through CY 5032 Week 48 • Time to the first hospitalization from Day 1 in CY 5031 through CY 5032 Week 48 • Time to recurrent hospitalizations from Day 1 in CY 5031 through CY 5032 Week 48
--	--

Overall Design:

CY 5032 is an open-label extension with the selective fast skeletal muscle troponin activator, reldesemtiv, in patients with ALS who finished dosing (through Week 48) in CY 5031 (COURAGE-ALS). Approximately 400 patients from the sites that participated in CY 5031 are expected to be enrolled in the open-label extension, CY 5032.

Following enrollment, patients will continue dosing with reldesemtiv, 300 mg twice a day for a 600 mg total daily dose (TDD) for a period of 48 weeks; however, a patient down-titrated for any reason to 150 mg twice daily in CY 5031 will continue with the down-titrated dose in CY 5032. Reldesemtiv should be taken twice daily, morning and afternoon (at least 8 hours apart).

At the end of 48 weeks, patients may transition to a reldesemtiv Managed Access Program (MAP). If the treating physician agrees to participate in the program, the treating physician's patient(s) may be eligible to transition from the OLE to the MAP.

Study Visits:

Patient visits will occur as follows (6 in clinic, 2 remote lab visits, and 8 remote visits):

- Day 1 (will be dependent upon protocol approval at the site, can be Week 48 or Week 52 visit for CY 5031 or later when approval is received)
- End of Week 4 (remote visit)
- End of Week 6 (remote lab visit)
- End of Week 8 (remote visit)
- End of Week 12 (in clinic)
- End of Week 16 (remote visit)
- End of Week 18 (remote lab visit)
- End of Week 20 (remote visit)
- End of Week 24 (in clinic)
- End of Week 28 (remote visit)
- End of Week 32 (remote visit)
- End of Week 36 (in clinic)
- End of Week 40 (remote visit)
- End of Week 44 (remote visit)
- End of Week 48 (in clinic)

- FU: End of Week 52 (in clinic)

If a patient decides to discontinue reldesemtiv, the patient will come into the clinic for the Reldesemtiv Discontinuation Visit as soon as possible after the last dose was taken.

Study Center(s):

Patients will be enrolled from approximately 85 clinical trial sites in the US, Canada, Europe, and Australia.

Assessments:

The following assessments will be performed:

- Collection of Demographic Data
- Physical Exam / Neurological Exam
- Vital Signs
- Clinical Safety Labs
- Serum Pregnancy Test for Women of Childbearing Potential
- ALSFRS-R
- AE evaluation and concomitant medication assessment (since last visit)

Eligibility Criteria:

Key Inclusion Criteria

- Able to comprehend and willing to sign an Informed Consent Form (ICF). If patient is able to comprehend, but non-written consent is given, an impartial witness must sign the ICF form
- Completed dosing in CY 5031

Key Exclusion Criteria

- Has taken an investigational study drug (other than reldesemtiv) prior to dosing, within 30 days or five half-lives of the prior agent, whichever is greater

Investigational Product:

Reldesemtiv will be administered as 150 mg tablets, at a dose of 300 mg twice a day for a 600 mg TDD.

Reldesemtiv tablets will be supplied to the clinical site in bottles. Patients will receive one or more bottles of study drug (reldesemtiv) at each clinic visit.

Patients must interrupt reldesemtiv for certain specified laboratory abnormalities until the laboratory value in question has returned to the threshold specified in the protocol for re-initiation of treatment. Patients must then resume dosing at 1 tablet twice a day thereafter (150 mg twice daily). Patients also may be down-titrated to 1 tablet twice a day by the Investigator in the case of adverse events felt to be related to study drug. Once patients have been down-titrated to one tablet twice daily for any reason, their dose may not be returned to two tablets twice daily.

Patients who experience a laboratory abnormality requiring interruption of reldesemtiv while receiving 150 mg twice daily may resume reldesemtiv 150 mg twice daily once the laboratory value in question has returned to the threshold specified in the protocol for re-initiation of reldesemtiv; however, should the same laboratory abnormality requiring interruption of reldesemtiv recur, the patient must be permanently discontinued from reldesemtiv.

Statistical Methods:

Unless specified otherwise, efficacy analyses will be performed to compare early-start and delayed-start treatment groups based on the data collected during CY 5031 from the patients in the full analysis set (FAS) of CY 5031 plus the data collected during CY 5032 from the patients who were in the FAS of CY 5031 and enrolled into CY 5032.

The combined assessment of change in ALSFRS-R total score, time to dependence on assisted ventilation, and survival time from baseline of CY 5031 through CY 5032 Week 48 will be analyzed using the joint-rank test. A stratified Wilcoxon test will be applied to compare the standardized joint ranks between the early-start and delayed-start treatment groups with adjustment for riluzole and edaravone use at CY 5031 baseline. The stratified Mann-Whitney probability as well as the p-value will be presented.

If data permit, the analyses of change from baseline will be conducted using a Mixed Model for Repeated Measures (MMRM) based on a restricted maximum likelihood method (SAS[®] PROC MIXED default). The model terms will include early-start and delayed-start treatment groups, CY 5031 baseline ALSFRS-R total score, visit, riluzole use at CY 5031 baseline, edaravone use at CY 5031 baseline as well as the interaction terms of baseline-by-visit and treatment-by-visit. Least square means (LSM), LSM difference and the corresponding standard errors, 95% confidence intervals (CI) and p-values will be presented.

Slope endpoints will be analyzed using a mixed model which will include early-start and delayed-start treatment groups, CY 5031 baseline value, time from CY 5031 baseline, riluzole use at CY 5031 baseline, edaravone use at CY 5031 baseline as well as interaction terms for treatment-by-baseline, and treatment-by-time, assuming random slope effect. The estimated slope and the slope difference as well as their standard errors will be presented.

[figure not shown]
The time to event analyses will be conducted using proportional hazard Cox regression models and the Kaplan-Meier method. Time to event will be summarized by number of events, number of patients at risk, median, 95% CIs of median, and 1st and 3rd quartiles. Events and censored data points will be summarized by count and percentage. Hazard ratios between early-start and delayed-start treatment groups and the corresponding 95% CIs and p-values will also be presented. A negative binomial regression method will be used to analyze for time to recurrent hospitalizations. Number of hospitalizations and total number of days in hospital will be summarized descriptively.

Safety data will be analyzed descriptively in the safety analysis set of CY 5032, including all patients who take at least one dose of study drug. All AE terms will be coded using the Medical Dictionary for Regulatory Activities (MedDRA). Primary system organ class (SOC) and preferred term (PT) of the Treatment Emergent Adverse Events (TEAEs) will be tabulated by the early-start and delayed-start treatment groups. TEAEs will also be summarized by severity and relationship to study drug. AEs that led to early discontinuation from treatment or trial will be summarized.

General and additional analysis methods will be detailed in the SAP.

1.2. Schema

Figure 1: Study Schema

* Day 1 will be dependent upon protocol approval at the site; it can be Week 48 or Week 52 visit for CY 5031 or later when approval is received

1.3. Schedule of Activities

	Day 1 ¹	Week 4	Week 6	Week 8	Week 12	Week 16	Week 18	Week 20	Week 24	Week 28	Week 32	Week 36	Week 40	Week 44	Week 48	FU (or ED): Week 52*
In Clinic	X				X				X			X			X	X
Remote Visit		X	X	X		X	X	X		X	X		X	X		
Informed Consent ²	X															
Inclusion and Exclusion Criteria	X															
Demographics	X															
Physical Examination	X ²															X
Neurological Exam	X ²															X
Weight & BMI	X				X				X			X			X	X
Concomitant Med Review	X	X		X	X	X		X	X	X	X	X	X	X	X	X
Vital Signs	X				X				X			X			X	X
AE/SAE Evaluation	X	X		X	X	X		X	X	X	X	X	X	X	X	X
Clinical Safety Labs ³	X		X ⁴		X		X ⁴		X			X			X	X
Pregnancy test (WOCBP only)	X ⁵								X						X	
Study Drug Dosing	X	X		X	X	X		X	X	X	X	X	X	X	X	
ALSFRS-R	X	X		X	X	X		X	X	X	X	X	X	X	X	X
Hospitalizations	X	X		X	X	X		X	X	X	X	X	X	X	X	X
DME Use	X	X		X	X	X		X	X	X	X	X	X	X	X	X

ED=Early discontinuation; AE=adverse event; BMI=body mass index; SAE=serious adverse event; WOCBP=women of childbearing potential; ALSFRS-R=Amyotrophic Lateral Sclerosis Functional Rating Scale-Revised; DME=Durable Medical Equipment

*Drug dosing will not occur at the ED visit

1=Day 1 of CY 5032 may occur on the same day as the Week 48 Visit or the FU Visit of CY 5031 or as a separate Day 1 Visit unique to CY 5032 that occurs after the CY 5031 FU Visit. If Day 1 in CY 5032 occurs more than 6-weeks after completion of the FU Visit in CY 5031, the initial dose of study drug will not be taken by the patient until their safety lab results are available and the estimated Glomerular Filtration Rate (eGFR)_{CySC} ≥ 45 ml/min/1.73m² and eGFR_{Cr} ≥ 45 ml/min/1.73m², alanine aminotransferase (ALT)/aspartate aminotransferase (AST) <3 × upper limit of normal (ULN), and bilirubin is normal or if abnormal reported as non-clinically significant by the investigator.

2=Physical Exam and Neurological Exam: Day 1 exams are only required if the patient enrolls in the OLE on the same day as the Week 48 visit in CY 5031 or at a separate Day 1 Visit unique to CY 5032 that occurs after the CY 5031 FU Visit; however, if a patient enrolls in the OLE at the FU visit in CY 5031, these exams do not need to be repeated on Day 1 of the OLE.

3=Clinical safety labs to include: Chemistry (collected every 3 months): sodium, potassium gamma-glutamyl transferase, chloride, calcium, magnesium, phosphorus, urea nitrogen, creatinine, eGFR_{Cr} (calculated using CKD-EPI creatinine equation), Total protein, cholesterol, bicarbonate, total bilirubin, direct bilirubin, indirect bilirubin, CK, ALP, LDH, AST (SGOT), ALT (SGPT), Cystatin C, eGFR_{CysC} (calculated by CKD-EPI cystatin C equation), uric acid, albumin, triglycerides, and glucose

Urinalysis (collected every 3 months): specific gravity, pH, blood, protein, glucose, bilirubin, UPCR and microscopy

TSH on Day 1, bHCG as applicable for WOCBP, FSH as required to determine menopausal status at Day 1 per Appendix 3 ([Section 10.3](#)).

4=Remote clinical safety labs to include: Chemistry (collected at Week 6 and Week 18): ALP, ALT (SGPT), AST (SGOT), direct bilirubin, and total bilirubin. Remote clinical safety labs may be collected by a home health vendor in the patient's home, or in the clinic, or by another method approved by the Sponsor.

5=Pregnancy test: If a WOCBP has had a negative pregnancy test within 30 days, a pregnancy test is not needed on Day 1. If it has been >30 days, then it is required.

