7.3. Renal Function Monitoring and Study Drug Management

Reldesemtiv will be held if:

- Both $eGFR_{Cr}$ and $eGFR_{CysC} < 30.0$ ml/min/1.73m² or
- urine protein creatinine ratio (UPCR) is ≥ 3 mg protein/mg creatinine (or ≥ 339 mg protein/mmol creatinine)

Reldesemtiv may be restarted at half the dose, or 1 tablet twice a day (150 mg BID) when:

- Both $eGFR_{Cr}$ and $eGFR_{CysC}$ is > 40.0 ml/min/1.73m² and
- UPCR is ≤ 1.5 mg protein/mg creatinine (or ≤ 170 mg protein/mmol creatinine)

Serum cystatin C, $eGFR_{CysC}$, serum creatinine, and $eGFR_{Cr}$ will be obtained. These renal related laboratory results will be reviewed by the local investigator and the study drug should be held or restarted in the event the above criteria are met.

Abnormal renal function tests meeting the above criteria will be repeated. The site investigator and medical monitor should discuss and agree that study drug can be resumed or alternatively permanently discontinued. Agreement by the patient, site investigator, and medical monitor must occur for study drug to be resumed at a reduced dose.

1. If reldesemtiv is re-initiated, it must be at the lower dose of 150 mg BID,
or
2. If the abnormal renal function test requiring interruption of reldesemtiv occurred during administration of 150 mg twice daily, reldesemtiv 150 mg twice daily may be resumed once the laboratory value in question has returned to the threshold specified in the

protocol for re-initiation of reldesemtiv; however, should the same abnormal renal function test requiring reldesemtiv interruption recur, the patient must be permanently discontinued from reldesemtiv.

To accomplish this, the medical monitor may direct the laboratory assessments (serum cystatin C, eGFR_{CysC}, serum creatinine, eGFR_{Cr}, and UPCR) to be repeated as often as twice a week until a final disposition is reached (ie, re-initiation of study drug at 150 mg BID or permanent discontinuation) is reached.

Criteria for permanent discontinuation of study drug due to potential renal toxicity

Study drug **must** be discontinued permanently if the patient requires hemodialysis.

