7.4. Liver Function Monitoring and Study Drug Management

ALT, AST, alkaline phosphatase (ALP) and total (and if available, direct) bilirubin will be obtained in accordance with the schedule of events.

Patients with abnormal hepatic laboratory values [ie, ALP, AST, ALT, total bilirubin (TBL)] or signs/symptoms of hepatitis as described below meet the criteria for permanent discontinuation of reldesemtiv. Patients who meet the criteria for permanent discontinuation must not be re-challenged.

Criteria for permanent discontinuation of reldesemtiv due to potential hepatotoxicity

- Elevation of either AST or ALT according to the following schedule:

Baseline AST or ALT Value	AST or ALT Elevation
Any	>8 × ULN at any time
Any	>5 × ULN but <8 × ULN for ≥2 weeks
Any	>5 × ULN but <8 × ULN and unable to adhere to enhanced monitoring schedule
Any	>3 × ULN with clinical signs or symptoms that are consistent with hepatitis (such as right upper quadrant pain/tenderness, fever, nausea, vomiting, jaundice)

OR

- TBL >3 × ULN at any time

If any of the criteria above are met, reldesemtiv must be permanently discontinued.

Study drug **must** be also discontinued permanently if ALL of the criteria below are met:

- TBL >2 × ULN or international normalized ratio (INR) >1.5

AND

- increased AST or ALT from the relevant baseline value as specified below:

Baseline AST or ALT Value	AST or ALT Elevation
<ULN	>3 × ULN

AND

- no other cause for the combination of the above laboratory abnormalities is apparent. Important alternative causes for elevated AST/ALT and TBL values include, but are not limited to:
 - hepatobiliary tract disease
 - viral hepatitis (eg, Hepatitis A/B/C/D/E, Epstein-Barr Virus, cytomegalovirus, Herpes Simplex Virus, Varicella, toxoplasmosis, and Parvovirus)
 - right sided heart failure, hypotension, or any cause of hypoxia to the liver causing ischemia
 - exposure to hepatotoxic agents/drugs or hepatotoxins, including herbal and dietary supplements, plants and mushrooms
 - heritable disorders causing impaired glucuronidation (eg, Gilbert’s Syndrome, Crigler-Najjar syndrome) and drugs that inhibit bilirubin glucuronidation (eg, indinavir, atazanavir)
 - alpha-one antitrypsin deficiency
 - alcoholic hepatitis
 - autoimmune hepatitis
 - Wilson’s disease and hemochromatosis
 - nonalcoholic fatty liver disease including steatohepatitis
 - nonhepatic causes (eg, rhabdomyolysis, hemolysis)

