8. STUDY ASSESSMENTS AND PROCEDURES

There will be up to six clinic visits, two remote lab visits, and eight remote visits (that requires a phone or video call), with windows to aid in scheduling as shown in [Table 3](#). If a patient visit must be scheduled outside the visit window, the Medical Monitor should be contacted. If a patient is scheduled for an in-clinic visit outside the visit window, the ALSFRS-R should be obtained by phone or video call during the visit window when possible, while the other visit related procedures will be obtained outside of the visit window when the patient is seen in clinic. Day 1 anchors all subsequent study visits.

Table 3: CY 5032 Visit Windows

Visit	Visit Window
Start of Dosing (Day 1): clinic visit	
End of Week 4: remote visit	28 days \pm 4 days
End of Week 6: remote lab visit	42 days \pm 4 days
End of Week 8: remote visit	56 days \pm 4 days
End of Week 12: clinic visit	84 days \pm 4 days
End of Week 16: remote visit	112 days \pm 4 days
End of Week 18: remote lab visit	126 days \pm 4 days
End of Week 20: remote visit	140 days \pm 4 days
End of Week 24: clinic visit	168 days \pm 4 days
End of Week 28: remote visit	196 days \pm 4 days
End of Week 32: remote visit	224 days \pm 4 days
End of Week 36: clinic visit	252 days \pm 4 days
End of Week 40: remote visit	280 days \pm 4 days
End of Week 44: remote visit	308 days \pm 4 days
End of Week 48: clinic visit	336 days \pm 4 days
FU: End of Week 52: clinic visit	364 days \pm 4 days

Study procedures and their timing are summarized in the SoA ([Section 1.3](#)). If Day 1 in CY 5032 occurs more than 6-weeks after completion of the FU Visit (Week 52) in CY 5031, the initial dose of study drug will not be taken by the patient until their safety lab results are available and the $eGFR_{CysC} \geq 45 \text{ ml/min/1.73m}^2$ and $eGFR_{Cr} \geq 45 \text{ ml/min/1.73m}^2$, $ALT/AST < 3 \times ULN$, and bilirubin is normal or if abnormal reported as non-clinically significant by the investigator.

Prospective approval of a protocol deviation to recruitment and enrollment criteria, also known as a protocol waiver or exception, is not permitted.

Immediate safety concerns should be discussed with the Medical Monitor immediately upon occurrence or awareness to determine if the patient should continue or discontinue study drug.

Adherence to the trial design requirements, including those specified in the SoA ([Section 1.3](#)), is essential and required for trial conduct.

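### The first-dose lab check for late entrants is stricter than Sections 7.3 and 7.4 on eGFR and ALT/AST, but inconsistent with them on bilirubin (no ceiling) and UPCR (not listed)

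*Protocol*

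**What the plan says.** The check applies only to late entrants, meaning patients whose CY 5032 Day 1 comes more than 6 weeks after the CY 5031 follow-up visit. It appears in Protocol Section 1.3 footnote 1 and in Section 8, and is copied in the SAP Table 1 footnote. The first dose waits until the safety labs are back, eGFR is at least 45 ml/min/1.73m² by both creatinine and cystatin C, ALT/AST is below 3 × ULN, and "bilirubin is normal or if abnormal reported as non-clinically significant by the investigator".

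The rules for patients on drug are in Section 7:

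- **Hepatic (7.4).** One stand-alone ground for permanent discontinuation is "TBL >3 × ULN at any time". The section adds: "Patients who meet the criteria for permanent discontinuation must not be re-challenged".
- **Renal (7.3).** Drug is held if both eGFRs are below 30, or if "urine protein creatinine ratio (UPCR) is ≥ 3 mg protein/mg creatinine". On restarting, the text reads "Reldesemtiv may be restarted at half the dose, or 1 tablet twice a day (150 mg BID) when" both eGFRs exceed 40 and UPCR is at most 1.5 mg/mg.

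UPCR belongs to the clinical safety labs scheduled on Day 1: "Urinalysis (collected every 3 months): specific gravity, pH, blood, protein, glucose, bilirubin, UPCR and microscopy" (Section 1.3 footnote 3). The Week 6 and Week 18 remote labs are limited to "Chemistry (collected at Week 6 and Week 18): ALP, ALT (SGPT), AST (SGOT), direct bilirubin, and total bilirubin".

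**The concern.** A check made before the first dose, in patients who have been off drug for some time, would normally be at least as demanding as the rules for stopping drug once treatment is under way. For eGFR and transaminases it is. For bilirubin and UPCR it is not, and Section 2.3.1.1 names renal and hepatic findings as the risks that monitoring is meant to mitigate.

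Two kinds of patient could pass the check as worded:

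- one with total bilirubin above 3 × ULN that the investigator reports as not clinically significant, who at the same value on drug would have to stop for good;
- one with UPCR of 3 mg/mg or more who was never down-titrated and would start at 300 mg twice daily, where Section 7.3 would hold drug and allow a restart only at 150 mg twice daily.

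The eligibility criteria in Sections 5.1 and 5.2 do not close the gap, since they set no bilirubin or UPCR limit. At stake is the safety of a small number of patients. There is almost no effect on analysis: after termination, SAP Section 9 keeps only disposition, demographics and baseline characteristics, an AE overview and abnormal liver labs as tables.

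**Working it through.** The plan gives no figure to reproduce. The check consists of setting each lab-based rule in Sections 7.3 and 7.4 against the entry conditions and asking whether a patient who satisfies the conditions can still meet the rule. ALT/AST below 3 × ULN is taken to mean that both are below 3 × ULN. The hemodialysis criterion is left out because it is not a lab rule.

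| Rule | Relevant entry condition | Can a patient who passes still meet it? |
|---|---|---|
| AST or ALT >8 × ULN | <3 × ULN | No |
| AST or ALT >5 and <8 × ULN for 2 weeks or more | <3 × ULN | No |
| AST or ALT >5 and <8 × ULN, enhanced monitoring not possible | <3 × ULN | No |
| AST or ALT >3 × ULN with hepatitis signs or symptoms | <3 × ULN | No |
| TBL >2 × ULN or INR >1.5, with AST or ALT >3 × ULN and no other cause | ALT/AST <3 × ULN | No |
| **TBL >3 × ULN alone** | normal, or waived by the investigator | **Yes, if waived** |
| Both eGFRs <30 | both ≥45 | No |
| **UPCR ≥3 mg/mg** | none | **Yes** |

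The entry eGFR of 45 also exceeds the Section 7.3 restart level of 40. Below 3 × ULN the check is stricter than Section 7.4 on bilirubin too: any abnormal value needs the investigator's report, whereas Section 7.4 takes no action on bilirubin alone until it exceeds 3 × ULN.

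**Discretion on bilirubin.** In Section 7.4 the search for another cause, with Gilbert's syndrome among the examples, belongs only to the combined rule (bilirubin or INR together with transaminases). The rule at 3 × ULN alone has no such exception. The check therefore allows a judgement that Section 7.4 does not.

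**Time off drug at entry.** If CY 5031 dosing ended at Week 48 and follow-up was at Week 52, the minimum is (52 − 48) + 6 = 10 weeks, and late entrants exceed it.

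**Next scheduled samples after Day 1** (Section 8, Table 3):

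- Bilirubin, Week 6: 42 − 4 = 38 to 42 + 4 = 46 days.
- UPCR, "End of Week 12: clinic visit": 84 − 4 = 80 to 84 + 4 = 88 days, because the Week 6 labs include no urine test.

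**Units.** Assuming a creatinine molar mass of 113.12 g/mol, 3 mg/mg is 3 × 113.12 = 339.4 mg/mmol and 1.5 mg/mg is 169.7 mg/mmol. These agree with the 339 and 170 printed in Section 7.3.

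**The case against.** The best answer is that the check adds to Section 7 and does not replace it. It states what must be true before the first dose; it nowhere says that a patient who passes must be dosed, and nothing in it suspends Sections 7.3 or 7.4. These patients are continuing a drug they took for at least 24 weeks in CY 5031 (Section 2.3.1), so a hold rule and a stop rule that applies at any time can fairly be read as covering a known Day 1 result. The check also requires the safety labs, which include UPCR, to be available first, and Section 8.2.4 requires documented review of each report. On bilirubin, Section 7.4 counts elevations that prompt discontinuation among the clinically significant ones, and Section 8.3.1.3 lists TBL above 3 × ULN as a liver event of special interest. Calling such a value not clinically significant would sit badly with both.

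Most of this stands, and it keeps the point small. It does not remove the mismatch. Sections 7.1 to 7.4 are framed as holding, interrupting or discontinuing drug and do not say that they govern the first dose in the extension. The one place that does govern that dose lists its lab conditions and leaves these two out.

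A reader might infer that the check is looser than the stopping rules as a whole. The table shows otherwise. A reader might also take 38 to 46 or 80 to 88 days as the time an affected patient would spend on drug. The documents do not support that. These are gaps between scheduled samples; the Day 1 result is already known, Section 7.3 has qualifying renal tests repeated (as often as twice a week if the medical monitor so directs), and Section 8 sends immediate safety concerns to the medical monitor.

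**Conclusion.** The point holds as a minor inconsistency between sections. The first-dose check departs from Sections 7.3 and 7.4 in exactly two respects: a bilirubin waiver with no upper limit, and no mention of UPCR. A site relying on the check alone could start a patient whom Section 7 would stop or hold. Reading the check as authority to dose goes too far, because Section 7 can be read as already in force on Day 1.

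The size cannot be quantified. Two of the eight rules in the table remain open, but the ALT/AST tiers overlap, so that count is not a measure of risk. The documents give no frequency for late entry, for TBL above 3 × ULN or for UPCR of 3 mg/mg or more; the combination is presumably rare. The trial was terminated early (SAP Section 4.2), so little can change prospectively. The conclusion rests on the literal wording of the check and assumes no other document, such as the Study Manual, fills the gap.

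**What to change.** At the end of the check in Section 1.3 footnote 1 and in Section 8, add:

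> and no Section 7.3 hold criterion or Section 7.4 discontinuation criterion is met (in no case TBL >3 × ULN or UPCR ≥3 mg/mg); a patient with UPCR ≥3 mg/mg may start only when the Section 7.3 restart criteria are met, at 150 mg twice daily.

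Align the SAP Table 1 footnote. Take the UPCR units from Section 7.3, since Section 8.3.1.3 prints the same limit per gram of creatinine.

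A late entrant with UPCR above 1.5 but below 3 mg/mg could still start at the usual dose. That matches Section 7.3, which holds drug only from 3 mg/mg. Requiring 1.5 mg/mg or less of every late entrant would be a defensible but stricter choice.

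The cost is one clause in two protocol places and one SAP footnote. Protocol amendments need IRB/IEC approval (Section 10.1.1), so with the trial stopped the change belongs in any further amendment or in re-use of this template. The clinical downside is that a rare late entrant with a benign high bilirubin is not started, and one with a high UPCR waits for a repeat sample. On drug, Sections 7.4 and 7.3 would stop or hold those patients anyway.
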